3 STUDY DESIGN

This is an open-label, single-institution, Phase 2 study to determine the response rate of BXCL701 administered orally and daily, combined with pembrolizumab, in patients with

advanced solid cancers. The study will also assess other efficacy parameters, such as PFS, OS and DOR, as well as the safety the combined treatment. Bayesian optimal phase 2 (BOP2) design will be adopted to monitor efficacy. The study will consist of 2 stages:

[figure not shown]
- Lead-in Stage (first 6 patients enrolled) in which the safety and tolerability of the combination of BXCL701 administered orally twice a day on Days 1 to 14 of a 21day cycle plus pembrolizumab 200 mg administered intravenously (IV) on Day 1 every 21 days will be assessed and confirmed in patients with advanced solid cancers. The dose of BXCL701 will be 0.6 mg divided in two doses (0.3 mg twice a day).
- 2) Efficacy Stage (BOP2-Stage) in which patients with advanced solid cancers will be treated with BXCL701 combined with pembrolizumab. Patients enrolled to the Lead-in Stage will be also evaluated in the efficacy stage. Starting from Protocol version 7, new patients enrolled will be administered BXCL701 at the starting dose of 0.2 mg orally twice a day for the first 7 days. If well tolerated and in the absence of signs and symptoms of clinically significant hypotension the dose will be escalated to 0.3 mg orally twice a day.

During the Lead-in Stage, patients will be observed for dose-limiting toxicity (DLT) during Cycle 1. Six patients will be treated initially with 0.3 mg BXCL701 twice a day (Days 1 to 14) plus pembrolizumab 200mg:

- If > 1 of the 6 original patients has a DLT in Cycle 1, the dose will be considered above the maximum tolerated dose (MTD) and additional 6 patients will be treated at the 0.4 mg BXCL701 daily Days 1 to 14 dose level.
 - If ≤ 1 of the patients experience a DLT, the Efficacy Stage can commence
 - \circ If > 1 of the patients experience a DLT, a discussion will be held between the investigators and supporters as to how to proceed

The study schema is presented in Figure 1.

DLT = dose-limiting toxicity; pembro = pembrolizumab; PR, partial response; CR, complete response

All safety data from all patients, who received at least one dose of study drug will be included in safety analysis. Unless doses were held because of DLT, a patient must have

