received >70% of their BXCL701 in Cycle 1 (i.e., \geq 30 of 42 planned doses) with pembrolizumab dosed on Day 1 of Cycle 1 to be eligible for DLT assessment.

Toxicities will be assessed by the investigator using the National Cancer Institute Common Terminology Criteria for Adverse Events (NCI CTCAE), version 5. The relationship of an AE to combination therapy (i.e., attribution to BXCL701 and/or pembrolizumab) is to be assessed by the investigator using the criteria in the protocol (Section 5.3.1).

A DLT is defined as any of the following AEs occurring during Cycle 1, regardless of investigator attribution to study treatment, unless the AE can be clearly and incontrovertibly attributed to an extraneous cause (e.g., disease progression) by the Principal Investigator:

- Any Grade 4 laboratory abnormality, regardless of duration.
- Any Grade 3 laboratory abnormalities if associated with clinical symptoms regardless of duration
- Any Grade ≥3 non-hematologic AE, with the exceptions of Grade ≥3 nausea, vomiting, diarrhea, constipation, and fatigue, that resolves to Grade ≤1 within 72 hours with optimal medical management and/or supportive measures.
- Grade ≥3 thrombocytopenia with Grade >1 bleeding or requirement for platelet transfusion.
- Grade \geq 3 febrile neutropenia.
- Grade ≥ 3 fever.
- Grade ≥ 3 skin rash.
- Laboratory abnormalities meeting Hy's law criteria (aspartate aminotransferase [AST] or alanine aminotransferase [ALT] >3 × upper limit of normal [ULN] with concomitant total bilirubin >2 × ULN).
- Any toxicity resulting in \geq 30% held/skipped doses of BXCL701 during Cycle 1.
- Delay of Cycle 2 by ≥ 14 days due to toxicity.
- Any other significant toxicity considered by the investigator and supporter's medical representatives to be dose-limiting.

Efficacy Stage:

After assessment of the safety and confirmation of the BXCL701/pembrolizumab2 dose schedule to be used in the subsequent stage, the Efficacy Stage will begin. Eligible patients will receive oral BXCL701 daily on Days 1 to 14 of a 21-day cycle plus pembrolizumab 200 mg administered IV on Day 1 every 21 days.

Study Design Features (Both Stages):

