proposed to be 0.6 mg daily, i.e., the previously identified recommended Phase 2 dose. The dose will be divided into two doses (0.3 mg twice a day) to minimize the risk of hypotension. Based on a review of emerging data from the BXCL701 program, the dosing schedule in the Efficacy Stage will be modified to implement a step-up dosing schedule during Cycle 1. The intent of step-up dosing is to immediately address a potentially serious side effect of hypotension that appears most likely to occur during the first week of treatment in Cycle 1. BioXcel has evaluated BXCL701 0.4 mg total daily dose with pembrolizumab during Phase 1b of the prostate cancer study and it was well-tolerated, with no DLTs experienced. In the Phase 1b cohort, none of the three patients experienced adverse events consistent with cytokine activation considered related to BXCL701. Therefore, the Bioxcel program is incorporating a one-week lead-in dosing period of 0.2 mg BID to potentially mitigate the effects of cytokine activation, including hypotensive events, which seem to predominantly occur during the first week of treatment in patients starting with 0.3mg BID. Escalation to 0.3 mg BID in patients demonstrating tolerance after one week of treatment is important since it is the dose that was previously associated with objective responses during prior development of BXCL701. Therefore, starting from Protocol version 7, new patients enrolled will be administered BXCL701 at the starting dose of 0.2 mg orally twice a day for the first 7 days. If well tolerated and in the absence of signs and symptoms of clinically significant hypotension the dose will be escalated to 0.3 mg orally twice a day.

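### The 72-hour DLT exemption has no Grade 4 cap, so an isolated Grade 4 event of an exempt type is not a DLT by grade and, late in Cycle 1, is scored only by interpretation

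*Combined protocol and SAP*

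**What the plan says.** All of the DLT criteria are in Section 3. Grade ≥3 non-hematologic events count, "with the exceptions of Grade ≥3 nausea, vomiting, diarrhea, constipation, and fatigue, that resolves to Grade ≤1 within 72 hours". The only criterion written specifically for Grade 4 concerns laboratory values: "Any Grade 4 laboratory abnormality, regardless of duration".

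Three other criteria could score an exempt event indirectly:

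- a missed-dose criterion, with a threshold of 30% or more when toxicity is the cause: "held/skipped doses of BXCL701 during Cycle 1";
- a late-start criterion for the next treatment cycle: "Delay of Cycle 2 by ≥ 14 days due to toxicity";
- a discretionary criterion, which closes the list: "Any other significant toxicity considered by the investigator and supporter's medical representatives to be dose-limiting".

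An event clearly due to an extraneous cause is excluded throughout.

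Section 6.2 requires BXCL701 to be discontinued for a life-threatening adverse event, and Section 8.5.1 lists such an event among the withdrawal criteria. Neither makes an exception for the five exempt types. No DLT criterion names permanent discontinuation as such.

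DLTs in the first 6 patients are a primary objective (Section 2.1). More than one DLT among the 6 puts the dose above the MTD; where at most one "of the patients experience a DLT, the Efficacy Stage can commence". Section 7 also suspends accrual in the Efficacy Stage when the observed DLT rate exceeds 33%.

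**The concern.** A 72-hour allowance for gastrointestinal events and fatigue is reasonable at Grade 3, where supportive care may be all that is needed. Written as Grade ≥3, it also covers Grade 4. The definition then disagrees with the rest of the protocol: an event serious enough to end the drug need not be dose-limiting, while a brief Grade 4 laboratory value always is.

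The affected patient could stay in the DLT denominator and be counted as DLT-free. Both safety rules depend on small counts, so one patient can decide them. An event that ends treatment should be scored by rule rather than by interpretation.

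**Working it through.** **Inputs.** BXCL701 twice a day on Days 1 to 14 (Sections 3 and 6.1); missed-dose criterion of at least 30% and evaluability above 70% of Cycle 1 doses (Section 3); lead-in limit of more than 1 of 6 (Section 3); suspension above 33% (Section 7).

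**Step 1: the plan's own dose count.** The evaluability rule is illustrated as at least "30 of 42 planned doses". The ratio 30/42 = 71.4% does exceed 70%, but the schedule gives 14 × 2 = 28 doses, not 42. A count of 42 would need 21 × 2 or 14 × 3. I use 28. The step-up schedule changes the dose size, not the number of doses.

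**Step 2: when the missed-dose criterion scores a permanent stop.** The threshold is 0.30 × 28 = 8.4, so 9 missed doses are needed.

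| First dose not taken | Doses missed | Share of 28 | Scored? |
|---|---|---|---|
| Day 10 morning | 10 | 35.7% | yes |
| Day 10 evening | 9 | 32.1% | yes |
| Day 11 morning | 8 | 28.6% | no |
| Day 12 morning | 6 | 21.4% | no |
| Day 13 morning | 4 | 14.3% | no |
| Day 14 morning | 2 | 7.1% | no |
| Day 15 or later | 0 | 0% | no |

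A patient who stops from Day 11 has taken 20/28 = 71.4%, which is above 70%, and so remains evaluable.

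**Step 3: sensitivity of the Day 11 boundary.**

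- One earlier dose missed because of toxicity gives 8 + 1 = 9 of 28, and the patient is scored.
- If 42 is used as denominator with 28 real doses, 0.30 × 42 = 12.6, so 13 missed doses are needed. The gap then opens with a stop from Day 9 (12/42 = 28.6%).
- If doses lost to permanent discontinuation do not count as held or skipped, the criterion never applies and the gap covers all of Cycle 1.

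**Step 4: the Cycle 2 criterion.** An event that starts on Day 21 and settles within 72 hours is over by about Day 24, so the event itself cannot cause a 14-day delay. The criterion applies only if a Cycle 2 that never starts is read as a delay. That reading is natural, but the protocol does not state it.

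**Step 5: what one unscored patient would change.** The lead-in decision changes only if exactly one of the other five patients has a DLT. With a common, independent DLT rate p, that probability is 5p(1 − p)⁴. The rates are assumptions; the documents give none.

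| Assumed p | 5p(1 − p)⁴ |
|---|---|
| 5% | 0.20 |
| 10% | 0.33 |
| 20% | 0.41 |
| 30% | 0.36 |

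These figures are conditional on one such patient occurring and going unscored. The unconditional effect is smaller by that unknown probability.

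If the 33% rule is applied per cohort, which Section 7 does not state, one patient separates 6/17 = 35.3% from 5/17 = 29.4%. At 9 patients it separates 3/9 = 33.3% from 2/9 = 22.2%, but 3/9 triggers suspension only if the limit is read as 0.33 rather than one third.

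**The case against.** The strongest reply is that hardly any real event would escape. Grade 4 laboratory abnormalities, and Grade 3 ones with symptoms, are DLTs whatever their duration. Any other Grade ≥3 non-hematologic event outside the five types also counts. Section 5.3.1 asks investigators to record a disease or syndrome, where possible, rather than its symptoms. Severe diarrhea from colitis (a pembrolizumab toxicity named in Section 1.4), or vomiting with hypovolemia (characteristic of BXCL701 according to Section 3.1), would therefore usually bring in a non-exempt term. **This stands**, and it limits the point to an isolated exempt event.

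The reply continues that people would catch what the wording misses. A life-threatening event is an SAE and goes to the IND Office regardless of attribution (Section 5.3.2). IND Office approval is needed before the Efficacy Stage (Section 7). The last DLT criterion lets the investigator and the supporter's medical representatives score it. **This largely stands:** they probably would. None of these safeguards makes scoring mandatory, however.

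Finally, the protocol cites CTCAE version 5 without reproducing it. The documents therefore do not show which of the five terms can reach Grade 4, or that Grade 4 means life-threatening. **This stands** as a stated assumption. The wording Grade ≥3 itself allows for grades above 3.

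**Conclusion.** The wording gap is real but narrow. It concerns an event of one of the five types that:

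- reaches Grade 4 and returns to Grade 1 or lower within 72 hours;
- leads to a stop from Day 11, or occurs on Days 15 to 21;
- comes with no qualifying laboratory finding and no other Grade ≥3 non-hematologic event;
- follows no earlier toxicity-related missed dose.

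It rests on the two grading assumptions, on 28 planned doses, and on counting doses lost to a permanent stop as held or skipped. Such events are likely rare. Their rate, and so the unconditional effect on either safety rule, cannot be quantified from the documents.

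Three stronger readings are tempting and are not supported:

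- A reader might infer that half of Cycle 1 is unprotected, because Days 11 to 21 are 11/21 = 52% of its days. That is a share of the calendar, not of events. Section 3.1 says of hypotensive events, "which seem to predominantly occur during the first week of treatment", and hypotension is not exempt in any case.
- A reader might infer that every late life-threatening event escapes the DLT list. The laboratory and other non-hematologic criteria rule that out.
- A reader might infer that the lead-in decision was wrong. The documents report no lead-in results.

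This is a cheap improvement of low priority.

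**What to change.** In the exemption only, replace Grade ≥3 by Grade 3. Grade 4 non-hematologic events then always count as DLTs on any day of Cycle 1, subject to the existing exclusion for extraneous causes.

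No added sentence about failure to start Cycle 2 is needed. The grade cap closes this gap by itself, and a general clause of that kind could turn elective stops for low-grade toxicity into automatic DLTs.

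Apply the new wording prospectively. If the lead-in has already been scored, check whether any of those 6 patients had such an event.

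The cost is one symbol in the text and no new data. The downside is a very slightly higher scored DLT rate, and with it a very slightly higher chance of de-escalating the dose or suspending accrual.

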6.5 Pembrolizumab Administration, Dose Modifications and Discontinuation

Pembrolizumab will be prepared, stored, and administered according to the current full Prescribing Information. Pembrolizumab will be obtained from commercial supplies and will be administered 200 mg intravenously over 30 minutes through a 0.2 to 5 micron sterile, nonpyrogenic, low-protein binding online or add-on filter. No other medication will be infused through the infusion line. Infusion will be interrupted and slowed for grade 1 or 2 infusion-related reactions and permanently discontinued for grade 3 or 4 infusion-related reactions. Pembrolizumab will be administered until disease progression, unacceptable toxicity, or withdrawal of consent.

AEs associated with pembrolizumab exposure may be immune-mediated. Immune-related AEs may occur any time after pembrolizumab administration and may affect multiple body systems. Early recognition and treatment are important to reduce complications. Most immune-related AEs are reversible and can be managed with discontinuation of pembrolizumab and initiation of steroids. Refer to the current regional pembrolizumab full Prescribing Information for recommended dose modifications for the management of toxicities (including immune-mediated reactions and infusion-related reactions) considered related to pembrolizumab. Patients who require a dose hold of pembrolizumab of \geq 42 days will be discontinued from the study.

Pembrolizumab should not be used in conjunction with other immunosuppressive agents other than corticosteroids administered for control of immune reactions considered related to pembrolizumab. Refer to the current regional pembrolizumab full Prescribing Information for further details.

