7 DATA ANALYSIS AND STATISTICAL CONSIDERATIONS

This is a phase 2, single center, basket study of oral BXCL701 daily on days 1-14 in combination with intravenous PD1/PDL1 antibody on day1 of 21-day cycle in subjects with advanced and refractory malignancies. Lead-in cohort will enroll 6 patients. Only the 6 patients treated at the selected dose during safety lead-in will be assigned to Cohort A or B as appropriate. That is, if there is a dose de-escalation during safety lead-in, then the 6 patients treated at the higher dose will not be assigned to the phase II cohorts. Cohorts A and B will enroll 9 to 17 patients. Response assessments with CT and/or MRI will be done every 9 weeks (3 cycles) following RECIST and iRECIST criteria.[19, 20] Intervals can be shortened to 6 weeks (2 cycles) if clinically necessary per treating physician.

The study will follow the BOP2 design with the following operating characteristics.

Power: 0.80

Type I error: 0.05

P0:0.05**P1:**0.25

Each cohort will enroll 9 patients. If there is no complete (CR) or partial response (PR) in the first 9 patients the enrolment to that cohort will stop. If there ≥ 1 PR or CR in the first 9 patients the enrollment will continue to enroll total of 17 patients. PR or CR does not require confirmation. The treatment will be considered promising for further exploration if ≥ 3 CRs or PRs are observed in 17 patients. The expected **Sample Size** will range from 9 (if terminated after safety lead in) to 34 patients. Accounted for ~20% of patients not being evaluable for efficacy, the actual number of patients to be recruited for the trial will range from 11 to 42.

Scenarios (PA, PB)	Pr(reject H0 for cohort A)	Pr(reject H0 for cohort B)	Average sample size for cohort A	Average sample size for cohort B
(0.05,0.05)	0.046	0.046	12.0	12.0
(0.05,0.25)	0.046	0.813	12.0	16.4
(0.25,0.25)	0.813	0.813	16.4	16.4
(0.05,0.15)	0.046	0.455	12.0	15.1
(0.15,0.15)	0.455	0.455	15.1	15.1
(0.15,0.25)	0.455	0.813	15.1	16.4

Operating characteristics:

Note: PA is the response rate for cohort A, PB is the response rate for cohort B.

The Investigator is responsible for completing toxicity/efficacy summary reports and submitting them to the IND office Medical Affairs and Safety Group for review. These should be submitted as follows:

• Lead-In Stage:

After the first 6 evaluable patients, complete cycle 1 of study treatment. IND Office approval must be obtained prior to advancing to the efficacy stage.

• Efficacy Stage:

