Abbreviations: BP = blood pressure; CxDx = Cycle (number) Day (number); CBC = complete blood count; CT = computed tomography; ECOG = Eastern Cooperative Oncology Group; EOT = End of Treatment; FU = follow-up; HR = heart rate; MRI = magnetic resonance imaging; RR = respiratory rate.

a. After discontinuation of study drugs, patients will complete an EOT visit within 21 days after the last study drug dose.

Protocol 2019-0748 08 Apr 2022

- b. A Safety Follow-up Visit is to be conducted 30 days (±7 days) after the last dose of study drug and later if drug-related AEs have not resolved at that time. Thereafter, patients without documented disease progression (PD) will be followed every 90 days for disease assessments until documentation of PD. After documentation of PD, patients will be followed every 90 days for survival status; such follow-up will likely be conducted by telephone.
- c. Day 1 of Cycle 2 and all subsequent cycles will be 21 days (± 3 days) after the previous dose of study drug was administered.
- d. Tumor assessment must include cross-sectional imaging (MRI or CT scanning with intravenous contrast whenever possible) of the chest/abdomen/pelvis plus whole-body bone scan. Other body sites (e.g., neck) to be included as clinically indicated. Tumor assessment to be performed at Screening, C4D1 (±7 days), C7D1 (±7 days), C10D1 (±7 days), and Day 1 (±7 days) of every 3rd cycle thereafter and at EOT. Intervals for scans can be shortened to 6 weeks (e.g. C3D1, C5D1 etc.) if clinically necessary per treating physician.
- e. Serum chemistry to include: sodium (Na), potassium (K), chloride (Cl), bicarbonate, calcium (Ca), magnesium (Mg), phosphate, blood urea nitrogen (BUN)/creatinine (Cr), and lactate dehydrogenase (LDH).
- f. Liver function tests include aspartate aminotransferase, alanine aminotransferase, alkaline phosphatase, total bilirubin, and albumin.

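### The lead-in report is due when 6 patients complete Cycle 1 (Day 21), but one listed DLT, a toxicity delay of Cycle 2 of 14 days or more, cannot be determined until about Day 36

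*Combined protocol and SAP*

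**What the plan says.** Section 3 states that in the Lead-in Stage "patients will be observed for dose-limiting toxicity (DLT) during Cycle 1". Its definition opens in the same terms: "A DLT is defined as any of the following AEs occurring during Cycle 1". One item on the list that follows is "Delay of Cycle 2 by ≥ 14 days due to toxicity".

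The dose rule in Section 3 is also tied to Cycle 1. If more than 1 "of the 6 original patients has a DLT in Cycle 1, the dose will be considered above the maximum tolerated dose", and 6 more patients are treated at 0.4 mg daily. With at most 1 DLT the Efficacy Stage may start.

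Section 7 times the lead-in report as follows: "After the first 6 evaluable patients, complete cycle 1 of study treatment". It adds that "IND Office approval must be obtained prior to advancing to the efficacy stage". Under Section 3, whether a patient can be assessed for DLT depends only on Cycle 1 dosing: more than 70% of BXCL701, and pembrolizumab on Day 1. No section says how to count a patient whose Cycle 2 is on hold when the report falls due.

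**The concern.** The list contains an item that can be met only after Cycle 1, while the observation period, the counting rule and the report trigger all stop at the end of Cycle 1. Followed literally, the report can be written, and the decision taken, before one of the protocol's own criteria can be answered for every patient.

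Evaluating DLTs in the first 6 patients is a primary objective, and one patient separates starting the Efficacy Stage from declaring the dose above the MTD. With one DLT recorded and one patient on hold, the report can read 1 of 6 and become 2 of 6 about two weeks later. The words tying a DLT to Cycle 1 add a second difficulty: someone could argue that a delay completed on Day 36 never counts. The same gap would apply to a second group of 6 at 0.4 mg daily.

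**Working it through.** The plan gives no operating characteristics for the lead-in rule, so there is no stated figure to reproduce.

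**1. Dates.** Inputs are the 21-day cycle (Section 6), the visit window in Appendix A, footnote c ("Day 1 of Cycle 2 and all subsequent cycles will be 21 days (± 3 days"), and the 14-day item in Section 3. I read the 21 days as running from Cycle 1 Day 1.

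- Cycle 1 ends on Day 21.
- Cycle 2 Day 1 = 1 + 21 = Day 22; with ±3 days, Day 19 to 25.
- The delay item is met at 22 + 14 = Day 36; with the window, Day 33 to 39.
- Gap from the end of Cycle 1 = 36 − 21 = 15 days; with the window, 12 to 18.

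**2. Who is affected.** The report waits for the sixth evaluable patient. For a patient who finished Cycle 1 *d* days before the sixth, the open time is max(0, 15 − *d*). At *d* = 0 it is 15 days, at *d* = 7 it is 8, and at *d* ≥ 15 it is 0 (*d* ≥ 18 with the window). Only the last patient has the full gap.

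**3. Whether other DLT items close it.** Most severe events are already DLTs within Cycle 1, but a route remains.

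- Section 6.2 holds BXCL701 for Grade 2 edema, hypotension, dizziness or hypovolemia, or another related Grade 2 event, until Grade 1 or baseline. It allows 6 weeks from onset for BXCL701-related events before permanent discontinuation.
- Twice-daily dosing on Days 1 to 14 is 28 doses. (Section 3 illustrates its 70% threshold with 42 planned doses; I use the percentage.)
- A hold starting on Day 11 misses 4 × 2 = 8 doses. 8/28 = 28.6%, below the 30% held-dose item. Doses taken are 20/28 = 71.4%, above the 70% needed for assessment.
- A Grade 2 event does not meet the Grade 3 items, and it may last until 11 + 42 = Day 53, beyond Day 36.

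If Cycle 2 is postponed for such an event, the delay is the only objective DLT item met. The documents do not say whether Cycle 2 could start with pembrolizumab alone, so this shows that the case can occur, not how often.

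**4. Effect on the rule, for illustration.** With complete counting, P(at most 1 of 6) = (1 − p)^6 + 6p(1 − p)^5. Assume a true DLT rate p = 0.33, and assume that a share s of DLTs shows only as a Cycle 2 delay. If only the last patient is unresolved, P = (1 − p)^5 + 5p(1 − p)^4(1 − p(1 − s)).

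| s | P(at most 1 of 6) |
|---|---|
| complete counting | 0.358 |
| 10% | 0.369 |
| 20% | 0.380 |
| 30% | 0.391 |

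The shift is 0.011 to 0.033, always toward starting the Efficacy Stage. The documents support no particular s.

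**5. Patients enrolled early.** No accrual rate is given. Assuming 1 to 4 patients per 30 days, 15 days is 0.5 to 2 patients, and 18 days is 0.6 to 2.4. Under the step-up in Sections 3 and 6.1, new patients take 0.2 mg twice daily for 7 days, which is 0.4 mg per day and equals the fallback dose. Within a 15-day window, only those enrolled in about the first 15 − 7 = 8 days would reach 0.3 mg twice daily before it closes.

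**The case against.** The best reply is that the plan is silent here rather than wrong. The report comes after Cycle 1 with no deadline, IND Office approval must follow, and any preparation and review time shortens the gap. Section 3 also opens the Efficacy Stage only after safety has been assessed and the dose schedule confirmed, and a patient on hold is visibly not fully assessed from about Day 22. The investigator and the supporter may call any significant toxicity dose-limiting. BXCL701 stops on Day 14, and Section 3.1 says that its characteristic events usually resolve once the drug is held.

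Most of this stands as a limit on size. It does not remove the conflict, because none of these provisions requires anyone to wait for the patient on hold, and the one stated trigger is completion of Cycle 1.

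Section 7 also suspends accrual in the Efficacy Stage if the DLT rate exceeds 33%. That is a partial backstop: 2/6 = 33.3% would trip it, but with one more DLT-free patient in the denominator 2/7 = 28.6% would not.

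A reader might go further and use Section 6.5, where pembrolizumab patients held for at least "42 days will be discontinued from the study", to conclude that Cycle 2 may restart as late as 22 + 41 = Day 63. The documents do not say that a pembrolizumab hold postpones Cycle 2, or from which date the 42 days run, so I place no weight on it.

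**Conclusion.** The point holds as a minor one. A stated decision trigger (Day 21) precedes the time at which a stated DLT criterion can be determined (about Day 36), and the wording that ties DLTs to Cycle 1 does not fit that criterion. A patient on hold for toxicity who meets no other item can be counted as DLT-free.

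The harm needs three things together: a hold unresolved at the report, no other DLT item met by that patient, and a count that this patient would move past 1 of 6. The gap is then at most 15 days (18 with the window), assuming no turnaround time for report and approval. Exposure is further limited by the 7 days at 0.2 mg twice daily.

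A reader might infer that a dose above the MTD would be carried through the trial, or that the plan instructs staff to count such a patient as DLT-free. The documents support neither. The hold is visible, nothing tells staff to count the patient that way, and the existing safeguards may catch the event, although they are not required to. Frequency cannot be estimated from the documents. The lead-in consequence disappears once all lead-in patients are classified. The Efficacy Stage 33% rule has no separate DLT definition, so the clarification would still help there.

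**What to change.** In Section 3, define the DLT period as Cycle 1 through the start of Cycle 2 or a 14-day Cycle 2 delay, whichever comes first, and say whether the 14 days run from Day 22 or from the end of the visit window. Have the rule of more than 1 in 6 count DLTs over that period instead of in Cycle 1 alone.

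In Section 7, make the lead-in report due only when each of the 6 evaluable patients has started Cycle 2, met a DLT criterion, reached the 14-day delay, or stopped treatment for a reason other than toxicity. Apply the same rule to a second group of 6 at 0.4 mg daily.

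The cost is a few sentences of text and a wait of up to about 15 to 18 days, incurred only when a patient's Cycle 2 is on hold for toxicity.
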